#### 9.1.9 Acute Physiologic and Chronic Health Evaluation II

The acute physiologic and chronic health evaluation (APACHE) II score (see appendix 15.3) will assess patients for the presence of multiple organ dysfunction and predict mortality by generating a point score ranging from 0 to 71 based on twelve physiologic variables, age and underlying health.

APACHE II will be assessed at Visit 2/Baseline, Visit 3/Day 3, Visit 4/Day 5, Visit 5/Day 7, Visit 6/Day 14, Visit 7/Day 21, Visit 8/Day 28/Early Termination and Visit 9/Day 90/Follow up.

#### 9.1.10 Lille Score

The Lille score is a composite score which predicts mortality in patients with AH who are not responding to steroid therapy. It is based on age, albumin, bilirubin (initial), bilirubin (day 7), creatinine and PT; a score of >0.45 identifies 75% of deaths, a score of >0.45 predicts a 6-month survival of 25%, and a score of <0.45 predicts survival of 85%.

Lille score will be assessed at Visit 2/Baseline, Visit 3/Day 3, Visit 4/Day 5, Visit 5/Day 7, Visit 6/Day 14, Visit 7/Day 21, Visit 8/Day 28/Early Termination and Visit 9/Day 90/Follow up.

#### 9.1.11 West Haven Criteria

The West Haven Criteria is used to classify the severity of hepatic encephalopathy with a grading of 1 – 4, Grade 1 being the least serious with the patient having a trivial lack of awareness to Grade 4 in which the patient is in a state of unconsciousness.

Grade	Criteria
1	Trivial lack of awareness Euphoria or anxiety Shortened attention span Impaired performance of addition
2	Lethargy or apathy Minimal disorientation of time or place Subtle personality changes Inappropriate behaviour
3	Somnolence to semi-stupor but responsive to verbal stimuli Confusion
4	Gross disorientation Coma (unresponsive to verbal or noxious stimuli)

(Ferenci et al. 1998)

West Haven criteria will be assessed at Visit 1/Screening , Visit 2/Baseline, Visit 3/Day 3, Visit 4/Day 5, Visit 5/Day 7, Visit 6/Day 14, Visit 7/Day 21, Visit 8/Day 28/Early Termination and Visit 9/Day 90/Follow up.

## 9.2 Safety Assessments

### 9.2.1 Medical History

A complete review of the patient's medical history will be undertaken by the Investigator or designee at the Visit 1/Screening and Visit 2/Baseline) to ensure that no exclusion criteria have been met.

Any concomitant disease, whether considered relevant for the study or not by the Investigator, must be reported in the CRF. The date of diagnosis or duration of the condition should be noted where possible. A history of alcohol abuse for > 6 months is key to qualify for the study.

### 9.2.2 Physical Examination

A physical examination, including height and weight, will be performed by the Investigator as per the Study Flow Chart (Appendix 1 and 2) at Visit 1/Screening, Visit 2/Baseline, Visit 3/Day 3, Visit 4/Day 5, Visit 5/Day 7, Visit 6/Day 14, Visit 7/Day 21, Visit 8/Day 28/Early Termination and Visit 9/Day 90/Follow up, in accordance with local practices.

A complete physical examination will be conducted at Visit 2/Baseline. At subsequent visits, the examination will be directed by patient symptoms and clinical features i.e., a standard panel of body systems will not be assessed unless indicated by patient. For example should the patient report to the investigator the presence of 'rash' then the skin would be evaluated. It is not required that additional body systems are assessed unless clinically warranted. Any abnormal results should be recorded in the CRF. Changes in findings of the physical examination compared with the baseline examination should be recorded as an AE.

### 9.2.3 Electrocardiogram

A 6-lead electrocardiogram (ECG) 10 mm/1 mV, 25 mm/s with a 10 second lead II rhythm strip will be recorded at each time point. ECGs will be recorded using the GE Mac 1200 or equivalent model. Patients will be rested quietly in a fully supine position for five minutes before the ECG is taken. Recordings will be made at Visit 1/Screening, Visit 2/Baseline and Visit 8/Day 28/Early Termination.

Use of a 12-lead ECG is acceptable if no 6-lead ECG is available.

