## 1.6 Previous Clinical Safety Studies with 15(S)-HEPE

The company sponsored a phase I study, DS102A-01 (EudraCT 2015-001153-33), a first in man study conducted in healthy volunteers, to assess the safety, pharmacokinetics and effect of food on orally administered DS102. DS102 (15(S)-HEPE EE) was administered to healthy volunteers in the following regimens: a single dose of 100mg, 500mg, 1000mg, or 2000mg under fasted conditions; a single 500mg dose under two fed conditions (standard diet and high fat diet); and as multiple doses of 500mg, 1000mg or 2000mg taken once daily for 28 consecutive days in a fasted state. In this study, 57 subjects (male and female) aged 18 to 45 years were enrolled with eight subjects (at least three males and three females per cohort) in each cohort. Subjects in each cohort were randomised in a ratio of 3:1 to receive either DS102 or placebo. Cohorts were commenced in a sequential manner starting with the 100mg, 500mg and 1000mg single dose cohorts in parallel and progressing to higher doses and multiple doses following evaluation by a safety monitoring committee (SMC).

This first in man study showed that DS102 overall had an excellent safety profile, a short elimination half-life of approximately two hours and a  $T_{max}$  of approximately four to eight hours. Results across dose levels studied showed high variability in the single and multiple dose cohorts and did not show a linear correlation between increasing dose and that of systemic exposure. The study demonstrated that administration with food increased the bioavailability of 15(S)-HEPE, as mean plasma concentrations of 15(S)-HEPE were higher under fed conditions compared to fasted conditions. There was no difference in bioavailability between normal and high fat diet fed conditions. DS102 was safe and well-tolerated in healthy subjects in this study with no serious adverse events (SAEs) reported.

The company is currently recruiting patients for two phase II studies, DS102A-02 (EudraCT 2016-000311-33), to assess the safety and efficacy of orally administered DS102 in NAFLD patients at doses of 1000mg or 2000mg per day, with placebo as a comparator and DS102A-03 (EudraCT 2016-002853-39), to assess the safety and efficacy of orally administered DS102 in COPD patients at doses of 1000mg or 2000mg per day, with placebo as a comparator. To date, DS102 has been well-tolerated with no related SAEs reported.

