### 8.2 Clinic Visits

A tabulated flow chart of the study is presented in Appendix 1 and 2.

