### **8.2.9 Visit 8/Day 28/Early Termination**

The following assessments will be performed:

- Physical examination (as detailed in Section 9.2.2)
- Vital signs (blood pressure, heart rate and body temperature), as detailed in Section 9.2.4);
- ECG (as detailed in Section 9.2.3)
- Pharmacokinetic sampling (as detailed in Section 9.2.8.1)
- Exploratory blood sampling (as detailed in Section 9.2.8.2)
- Samples for clinical laboratory safety tests (haematology, serum biochemistry, and coagulation tests as detailed in Section 9.2.5)
- Pregnancy test (as detailed in Section 9.2.7)
- MELD (as detailed in Section 9.1.1)
- MDF (as detailed in Section 9.1.7)
- m-SOFA (as detailed in Section 9.1.8)
- APACHE II score (as detailed in Section 9.1.9)
- Total bilirubin (as detailed in Section 9.1.2)
- CK-18 (as detailed in Section 9.1.6)
- AST:ALT (as detailed in Section 9.1.3)
- Child pugh score (as detailed in Section 9.1.5)

- Gamma GT (as detailed in Section 9.1.4)
- Biomarker (as detailed in Section 9.2.8.3)
- West Haven criteria assessment (as detailed in Section 9.1.11)
- Lille score assessment (as detailed in Section 9.1.10)
- Collection of acute kidney injury, ascites and variceal haemorrhage data
- AE assessment (as detailed in Section 11)
- Concomitant medication assessment (as detailed in Section 9.2.10)

In addition, the following assessments of nutritional status will also be performed, with nutritional interventions provided where required:

- BMI
- Bedside Subjective Global Assessment (SGA) score (0, 1, 2, and 3). Patients will be classified into the following categories:
  - Well nourished (0)
  - Mild malnutrition (1)
  - Moderate malnutrition (2)
  - Severe malnutrition (3)

The IMP or placebo will be returned. Further IMP or placebo will not be supplied to the patient.

On completion of this visit, patients will be advised that they will be required to return to the investigational site in 62 days at Visit 9 for final assessment.

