### **8.2.10 Visit 9/Day 90/Follow Up**

In case of the patient's survival the following assessments will be performed:

- Physical examination (as detailed in Section 9.2.2)
- Vital signs (blood pressure, heart rate and body temperature), as detailed in Section 9.2.4);
- Samples for clinical laboratory safety tests (haematology, serum biochemistry, and coagulation tests as detailed in Section 9.2.5)
- MELD ( as detailed in Section 9.1.1)
- MDF (as detailed in Section 9.1.7)
- m-SOFA (as detailed in Section 9.1.8)
- West Haven criteria assessment (as detailed in Section 9.1.11)
- Lille score assessment (as detailed in Section 9.1.10)
- APACHE II score (as detailed in Section 9.1.9)
- Total bilirubin (as detailed in Section 9.1.2)
- CK-18 (as detailed in Section 9.1.6)

---

- AST:ALT (as detailed in Section 9.1.3)
- Child pugh score (as detailed in Section 9.1.5)
- Gamma GT (as detailed in Section 9.1.4)

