## 15. 2 Appendix 2: Study Flowchart – Double-Blind Phase

Visit	Screening/ Visit 1	Baseline/ Visit 2	Day 3/ Visit 3	Day 5/ Visit 4	Day 7/ Visit 5	Day 14/ Visit 6	Day 21/ Visit 7	Day 28/Visit 8/ Early Termination	Day 90/Visit 9/ Follow Up
Day		0	3	5	7	14	21	28	90
Visit Window	N/A	±0 day	±0 day	±0 day	±2 day	±2 day	±2 day	±1 day	±10 days
Informed Consent 	X								
Inclusion/Exclusion	X	X							
Demographics	X								
Patient Randomisation		X							
Medical History	X	X							
Physical Examination	X	X	X	X	X	X	X	X	X
Vital Signs	X	X	X	X	X	X	X	X	X
ECG (6-lead or 12-lead)	X	X							X
Pharmacokinetic Sampling 		X	X	X	X	X	X	X	
Exploratory Blood Sample		X				X		X	
Clinical Laboratory Tests 	X	X	X	X	X	X	X	X	X
Virology	X								
Urinalysis	x								
Liver ultrasound	X								
Pregnancy Test 	X	X				X		X	
MELD	X	X	X	X	X	X	X	X	X
MDF	X	X	X	X	X	X	X	X	X
m-SOFA		X	X	X	X	X	X	X	X
West Haven Criteria	X	X	X	X	X	X	X	X	X
APACHE II		X	X	X	X	X	X	X	X
Lille score		X	X	X	X	X	X	X	X
Total Bilirubin	X	X	X	X	X	X	X	X	X
CK-18		X	X	X	X	X	X	X	X
ALT, AST	X	X	X	X	X	X	X	X	X
Child Pugh Score		X	X	X	X	X	X	X	X
Gamma GT		X	X	X	X	X	X	X	X
Assessment of nutritional status		X				X		X	
Collection of acute kidney injury, ascites and variceal haemorrhage data		X	X	X	X	X	X	X	
Biomarker		x	x	x	x	x	x	x	

Visit	Screening/ Visit 1	Baseline/ Visit 2	Day 3/ Visit 3	Day 5/ Visit 4	Day 7/ Visit 5	Day 14/ Visit 6	Day 21/ Visit 7	Day 28/Visit 8/ Early Termination	Day 90/Visit 9/ Follow Up
Mortality			X	X	X	X	X	X	X
IMP/Placebo Administration		X -----X							
AE Assessment		X	X	X	X	X	X	X	
Concomitant Medication Assessment	X	X	X	X	X	X	X	X	

 Includes biochemistry, haematology, and coagulation tests. Caeruloplasmin will be collected at screening only

 Female Patients of child bearing potential only.

 Patient may be required to reconsent after Visit 1 if new information is made available.

 Trough plasma PK samples will also be obtained prior to the first daily dose on the indicated days.

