2.4 Visit Structure

During the study, 8 visits to the clinic are scheduled after the screening visit (Visit 1): one at the start of the comparative treatment period (Baseline/Visit 2) and six in the comparative treatment period (Visit 3/Day 3, Visit 4/Day 5, Visit 5/Day 7, Visit 6/Day 14, Visit 7/Day 21, Visit 8/Day 28 or Early Termination).

A final safety follow-up visit (Visit 9/Day 90) will be conducted on Day 90.

Both the pilot and main, double-blind, phase will follow the same structure.

Full details of the visit structure and scheduled assessments are detailed in the study protocol section 8 Study Conduct and Appendices 1 and 2.

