6.19 Electrocardiography

The overall interpretation of the ECG (Normal, Abnormal Not Clinically Significant (NCS), and Abnormal Clinically Significant (CS)) will be summarised over time.

All ECG data will be listed.

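### Appendix 2 puts the only post-baseline ECG of the double-blind phase at Day 90, while sections 9.2.3 and 8.2.9 and Appendix 1 put it at Day 28/Early Termination

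*Protocol*

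**What the plan says.** The protocol schedules the ECG in five places.

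- Section 9.2.3 (Electrocardiogram): "Recordings will be made at Visit 1/Screening, Visit 2/Baseline and Visit 8/Day 28/Early Termination".
- Section 8.2.9 (Visit 8/Day 28/Early Termination) includes an ECG, with a cross-reference to 9.2.3.
- Section 8.2.10 (Visit 9/Day 90) opens with "In case of the patient's survival the following assessments will be performed". The list that follows has no ECG.
- Appendix 1 (pilot phase) marks the ECG at Screening, Baseline and Day 28.
- Appendix 2 (double-blind phase) marks it at Screening, Baseline and Day 90. The Day 28 cell is empty.

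Section 8.2 introduces the charts with "A tabulated flow chart of the study is presented in Appendix 1 and 2". SAP 2.4 takes its schedule from protocol section 8 and from both appendices, and adds "Both the pilot and main, double-blind, phase will follow the same structure".

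On analysis, SAP 6.19 states: "The overall interpretation of the ECG (Normal, Abnormal Not Clinically Significant (NCS), and Abnormal Clinically Significant (CS)) will be summarised over time". Protocol 12.7 describes the ECG summary as being by treatment and by day. SAP 6.5 tabulates only scheduled post-baseline ECG values; repeat and unscheduled ones are listed but left out of the tables.

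**The concern.** Appendix 2 is the working schedule for the only phase with a placebo arm. A site that follows it would take no ECG between the first dose and Day 90. The empty cell is also the Early Termination column, so patients who stop early, including those who stop for an adverse event, would have no ECG at that visit either. An ECG missed at the end of treatment cannot be recovered later.

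The conflict carries into the SAP. The tables admit only scheduled ECGs, and the sources that SAP 2.4 cites for the schedule disagree about which post-baseline ECG is scheduled. SAP 6.19 names no visit, so it does not settle the matter.

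**Working it through.** The plan gives no figure to reproduce here. The check is a side-by-side reading plus one date calculation.

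**Post-baseline ECG, source by source**

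| Source | Day 28/Early Termination | Day 90 |
|---|---|---|
| Protocol 9.2.3 | yes | no |
| Protocol 8.2.9 (Visit 8 list) | yes | – |
| Protocol 8.2.10 (Visit 9 list) | – | no |
| Appendix 1 (pilot) | yes | no |
| Appendix 2 (double-blind) | no | yes |

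**Position of the marks.** Both charts have nine visit columns: Screening, Baseline, Days 3, 5, 7, 14, 21, 28 and 90. The row labelled "ECG (6-lead or 12-lead)" has all nine cells in each chart. The marks are in cells 1, 2 and 8 in Appendix 1 and in cells 1, 2 and 9 in Appendix 2. As a control, the pregnancy-test row of Appendix 2 has its marks at Screening, Baseline, Day 14 and Day 28, which matches section 9.2.7. The columns of that table are therefore not shifted as a whole.

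**Distance of a Day 90 ECG from treatment.** Inputs:

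- Section 10.2 puts the last dose on the day before the Day 28 visit, so nominally Day 27. (That sentence calls the visit Visit 6; elsewhere Day 28 is Visit 8.)
- Appendix 2 gives Day 90 a window of ±10 days.

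Results:

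- Nominal: 90 − 27 = 63 days after the last dose.
- Earliest: (90 − 10) − 27 = 53 days.
- Latest: (90 + 10) − 27 = 73 days.

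The ±1 day window on the Day 28 visit moves each limit by at most one day. For a patient who stops treatment early, the gap to Day 90 is longer.

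**Who has each recording.** A Day 90 ECG requires the patient to be alive and to attend. The Day 28/Early Termination visit also covers patients who discontinue before Day 28 (sections 7.5 and 8.1). The two recordings therefore differ both in time since treatment and in the patients who contribute them.

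**Which recording is tabulated.** Under section 8 and Appendix 1, Day 28 is the scheduled ECG and a Day 90 ECG is unscheduled. Under Appendix 2 the reverse holds. By the rule in SAP 6.5, whichever counts as unscheduled is listed but not tabulated. The documents do not say whether text or chart prevails.

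**The case against.** The case for treating this as a small clerical slip is substantial.

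- **The text is explicit.** Sections 9.2.3 and 8.2.9 both cover the double-blind phase and both give Day 28/Early Termination. Sections 9.2.2, 9.2.4, 9.2.5 and 9.2.7 hand their timing to the flow chart, but 9.2.3 does not. Section 8.2 says only that a chart is presented. This stands. It means data are at risk only where a site follows the chart over the text.
- **The chart may have been misread.** In the text copy of these two tables, the row for study-drug administration is visibly damaged: its closing mark falls at Day 14 in Appendix 1, and the row collapses into one cell in Appendix 2. The ECG row is complete and the pregnancy-test row is correctly placed, so a real misplacement is more likely than a reading error. The printed page should still be checked.
- **The stakes are limited.** The safety endpoints in section 5.4 are treatment-emergent (serious) adverse events and SUSARs. ECG interpretation is summarised descriptively, with no planned test. This stands.
- **The loss should not favour one arm.** Section 12.2 stratifies randomisation by site, so a site-level omission should fall on both arms about equally. This limits bias from the omission but does not restore the missing recordings.

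A reader might infer that the DS102–placebo ECG comparison cannot be made, or that none of the 120 randomised patients would have an end-of-treatment ECG. Both would require every site to disregard two text sections, and nothing in the documents suggests that.

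A reader might also try to count patients with no post-baseline ECG from the background mortality in section 1.1 (above 30%). That figure has no time horizon. Patients who die before any Day 28 or Early Termination visit would lack the recording under either schedule. Only deaths and non-attendance after that visit could be attributed to the discrepancy, and the documents give no figure for them.

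Nor does the SAP pool visits. A summary over time, read with protocol 12.7, keeps Day 28 and Day 90 apart. The SAP's difficulty is only that it is unclear which ECG counts as scheduled.

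**Conclusion.** The point holds as an internal inconsistency that should be resolved. Appendix 2 disagrees with 9.2.3, 8.2.9, 8.2.10 and Appendix 1 on the single post-baseline ECG of the randomised phase. The consequence is possibly missing end-of-treatment and early-termination ECGs at sites that use Appendix 2, together with an undefined scheduled visit for the SAP table. The number of affected sites or patients cannot be estimated from the documents.

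A Day 90 recording is no substitute: it falls about 53 to 73 days after the last scheduled dose and comes only from attending survivors. This rests on two assumptions: that the last dose is on Day 27, as section 10.2 implies, and that the printed Appendix 2 shows the mark where the text copy places it. If the printed page has the mark at Day 28, the point falls away.

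**What to change.** 1. Check the ECG row on the printed page of Appendix 2.
2. If the discrepancy is confirmed, reconcile that row with 9.2.3, 8.2.9, 8.2.10 and Appendix 1 so that all give the same post-baseline ECG visit. Which visit is intended is for the sponsor to state.
3. If ECGs have already been recorded at differing visits, keep each under its actual visit in the SAP 6.19 table, as protocol 12.7 implies. State how they are treated under the scheduled-only rule of SAP 6.5. Do not substitute a Day 90 value for an end-of-treatment value.

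The cost is small. It is a correction to the schedule and, only if step 3 applies, a sentence in the SAP. Both versions of the schedule contain one post-baseline ECG per patient, so choosing one of them adds no procedure. Sample size, endpoints and the planned form of the ECG summary do not change.

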### 9.2.4 Vital Signs

Vital signs measurements will be performed as per the Study Flow Chart (Appendix 1 and 2) at Visit 1/Screening, Visit 2/Baseline, Visit 3/Day 3, Visit 4/Day 5, Visit 5/Day 7, Visit 6/Day 14, Visit 7/Day 21, Visit 8/Day 28/Early Termination and Visit 9/Day 90/Follow up.

Measurements to be taken include:

- Blood pressure: will be performed as supine (after at least five minutes of rest); systolic and diastolic blood pressure (in mmHg) will be recorded.
- Heart rate: taken at rest (in bpm).
- Temperature: will be taken as per clinic practice. Temperature and route will be recorded in the CRF.

Vital signs measurements will be performed before any blood samples are taken. All new findings or changes to previous findings considered clinically significant will be recorded in the CRF as an AE if the finding is made after the patient has signed the ICF.

### 9.2.5 Clinical Laboratory Safety Tests: Haematology, Serum Biochemistry, and Coagulation

Blood and urine samples will be taken as per the Study Flow Chart (Appendix 1 and 2) for routine haematology, serum biochemistry, coagulation. All samples will be analysed in a central laboratory.

Haematology: Full blood count to include red cell count, haemoglobin, haematocrit, white cell count, differential white cell count, platelet count and reticulocyte count.

Serum biochemistry: Urea (blood urea nitrogen (BUN)), creatinine, uric acid, total bilirubin, indirect and direct bilirubin, sodium, bicarbonate potassium, phosphorus, calcium chloride, alkaline phosphatase (ALP), AST, ALT, AST:ALT ratio, gamma GT, albumin, total protein, total cholesterol, triglycerides, glucose, C-reactive protein (CRP), plasma caeruloplasmin (screening only).

Coagulation: PT (prothrombin time), INR and APTT (activated partial prothrombin time)

### **9.2.6 Virology**

A blood sample will be taken to perform virology tests including human immunodeficiency virus (HIV), Hepatitis C and Hepatitis B as detailed in Study Flow Chart (Appendix 1 and 2)

### **9.2.7 Pregnancy Test**

For female patients of childbearing potential only, a pregnancy test will be carried out as per the Study Flow Chart (Appendix 1 and 2) at Visit 1/Screening, Visit 2/Baseline, Visit 6/Day 14 and Visit 8/Day 28/Early Termination.

### **9.2.8 Exploratory Blood Sampling**

Details of the volume of blood to be taken, sample preparation and handling are contained in a separate laboratory procedures manual.

Laboratory results will be reviewed for clinically significant values by each investigator following sample analysis and verification. The report must be signed and dated by the investigator before insertion in the eCRF.

Additional blood may be required for repeats of safety laboratory test.

#### **9.2.8.1 Pharmacokinetic sampling**

Blood samples for pharmacokinetic (PK) analysis will be collected via direct venepuncture as per the Study Flow Chart (Appendix 1 and 2) at Visit 2/Baseline, Visit 3/Day 3, Visit 4/Day 5, Visit 5/Day 7, Visit 6/Day 14, Visit 7/Day 21, and Visit 8/Day 28/Early Termination.

Trough plasma samples will be obtained from all patients (pilot and double blind phases) prior to first daily dose on the indicated days. Additional post-dose serial plasma samples will be obtained from the six patients on Days 0 and 7 of the preceding pilot phase for full PK characterisation at 0.5, 1, 2, 3, 4, 6, 7, 8, 10, and 12 (before next dose) hours post-dose.

A 1 mL blood sample will be taken at each time point. Following centrifugation, plasma samples will be split in two and a back-up sample will be handled as specified in Section 9.2.12 and described in the laboratory manual.

